10.6.1.3 Anti-rhHNS Antibody Formation

Anti-rhHNS antibody formation will be monitored throughout the study. Results will be presented in summary tables by assay methodology used to identify antibodies, number and percentage of positive and negative specimens by evaluation visit and/or study week, and number and percentage of positive and negative specimens overall. These results will also be presented in data listings.

10.6.2 Secondary Analysis

10.6.2.1 Clinical Assessments

The change from baseline in neurocognitive assessment based scores will be examined by dose group. Furthermore, the effect of rhHNS administration on QoL measures will be examined by presenting mean change from baseline across dose groups. Other relevant assessments which might help in the understanding of clinical activity will also be analyzed.

10.6.2.2 Pharmacodynamic Analyses

To determine the effects of rhHNS administration on biomarkers, mean change from baseline will be assessed at selected time points. The heparin sulfate reduction (in CSF and urine) will be examined using mean change and the corresponding 95% confidence interval. The concentration of inflammatory cytokines in serum and CSF will also be examined. Other exploratory biomarkers in CSF, serum, and urine may also be examined.

The effect of anti- rhHNS antibodies on the changes in CSF biomarkers may also be examined by presenting summary tables by antibody status.

The planned analyses and presentations will be defined in the Statistical Analysis Plan (SAP).

11 ADMINISTRATIVE CONSIDERATIONS

11.1 Investigators and Study Administrative Structure

Before initiation of the study, the Investigators must provide the Sponsor with a completed Form FDA 1572. Study medications may be administered only under the supervision of the Investigators listed on this form. Curriculum vitae must be provided for the Investigators and sub-investigators listed on Form FDA 1572.

The Investigator should ensure that all persons assisting with the study are adequately informed about the protocol, any amendments to the protocol, the study treatments, and their study related duties and functions. The Investigator must maintain a list of sub-investigators and other appropriately qualified persons to whom he or she has delegated significant study related duties.

11.2 Institutional Review Board (IRB) or Independent Ethics Committee (IEC) Approval

Before initiation of the study, the Investigator must provide the Sponsor with a copy of the written IRB/IEC approval of the protocol and the informed consent form. This approval must refer to the informed consent form and to the study title, study number, and version and date of issue of the study protocol, as given by the Sponsor on the cover page of the protocol.

Status reports must be submitted to the IRB/IEC at least once per year. The IRB/IEC must be notified of completion of the study. Within 3 months of study completion or termination, a final report must be provided to the IRB/IEC. A copy of these reports will be sent to the study clinical monitor. The Investigators must maintain an accurate and complete record of all submissions made to the IRB/IEC, including a list of all reports and documents submitted. AEs which are reported to the U.S. Food and Drug Administration (FDA) or other Regulatory agencies (Investigational New Drug [IND] Safety Reports) must be submitted promptly to the IRB/IEC.

11.3 Ethical Conduct of the Study

The procedures set out in this study protocol, pertaining to the conduct, evaluation, and documentation of this study, are designed to ensure that the Sponsor and Investigators abide by good clinical practice (GCP) as described in the 21 CFR Parts 50, 56, and 312 and the International Conference on Harmonisation (ICH) GCP Guidelines. Compliance with these regulations and guidelines also constitutes compliance with the ethical principles described in the Declaration of Helsinki (2008).

11.4 Patient Information and Consent

Before enrolling in the clinical study, the patient's parent(s), or the patient's legally authorized representative(s) must consent to participate after the nature, scope, and possible consequences of the clinical study have been explained in a form understandable to him or her. An informed consent form that includes information about the study will be prepared and given to the patient's parent(s), or the patient's legally authorized representative(s). This document will contain all FDA and ICH-required elements.

The informed consent form must be in a language understandable to the patient's parent(s), or the patient's legally authorized representative(s) and must specify who informed the patient's parent(s), or the patient's legally authorized representative.

After reading the informed consent document, the patient, patient's parent(s), or the patient's legally authorized representative(s) must give consent in writing. The patient's consent must be confirmed at the time of consent by the personally dated signature of the patient, patient's parent(s) or the patient's legally authorized representative(s) and by the personally dated signature of the person conducting the informed consent discussions. If the patient, patient's parent(s), or the patient's legally authorized representative(s) is unable to read, oral presentation and explanation of the written informed consent form and information to be supplied must take place in the presence of an impartial witness. Consent (or assent) must be confirmed at the time of consent orally and by the personally dated signature of the patient, patient's parent(s) or by the patient's legally authorized representative(s). The witness and the person conducting the informed consent discussions must also sign and personally date the informed consent document. It should also be recorded and dated in the source document that consent was given.

A copy of the signed and dated consent document(s) must be given to the patient's parent(s), or the patient's legally authorized representative(s). The original signed and dated consent document will be retained by the Investigator.

The Investigator will not undertake any measures specifically required solely for the clinical study until valid consent has been obtained.

A model of the informed consent form to be used in this study will be provided to the sites separately from this protocol. Where applicable, signed assent(s) to participate in the study must be obtained.

11.5 Patient Confidentiality

Patient names will not be supplied to the Sponsor. Only the patient number and patient initials will be recorded in the eCRF, and if the patient name appears on any other document, it must be obliterated before a copy of the document is supplied to the Sponsor. Study findings stored on a computer will be stored in accordance with local data protection laws. The patients will be told that representatives of the Sponsor, a designated CRO, the IRB/IEC, or regulatory authorities may inspect their medical records to verify the information collected, and that all personal information made available for inspection will be handled in strictest confidence and in accordance with local data protection laws. The Investigator will maintain a personal patient identification list (patient numbers with the corresponding patient names) to enable records to be identified.

11.6 Study Monitoring

Monitoring procedures that comply with current Good Clinical Practice (GCP) guidelines will be followed. On-site review of the eCRF's for completeness and clarity, cross-checking with source documents, and clarification of administrative matters will be performed.

The study will be monitored by the Sponsor or its designee. On site monitoring will be performed by a representative of the Sponsor (Clinical Study Monitor) who will review the CRFs and source documents. The site monitor will ensure that the investigation is conducted according to protocol design and regulatory requirements by frequent site visits and communications (letter, telephone, and facsimile).

11.7 Case Report Forms and Study Records

Case report forms are provided for each patient in electronic format. Electronic Data Capture (EDC) will be used for this study. The study data will be recorded from the source documents into the electronic clinical report form (eCRF). The electronic files will be considered as the CRFs.

All forms must be filled out by authorized study personnel. All corrections to the original eCRF entry must indicate the reason for change. The Investigator is required to sign the eCRF after all data have been captured for each patient. If corrections are made after review and signature by the Investigator, he or she must be made aware of the changes, and his or her awareness documented by re-signing the eCRF.

11.7.1 Critical Documents

Before Shire HGT initiates the trial (ie, obtains informed consent from the first patient), it is the responsibility of the Investigator to ensure that the following documents are available to Shire HGT or their designee:

- Curricula vitae of Investigator and sub-investigator(s) (current, dated and signed or supported by an official regulatory document)
- Current medical license of Investigator and sub investigator(s)
- Signed and dated agreement of the final protocol
- Signed and dated agreement of any amendment(s), if applicable
- Approval/favorable opinion from the IRB/IEC clearly identifying the documents reviewed: protocol, any amendments, Patient Information/Informed Consent Form (Assent form if applicable), and any other written information to be provided regarding patients recruitment procedures
- Copy of IRB/IEC approved Patient Information/Informed Consent Form (Assent Form if applicable)/any other written information/advertisement
- Any additional regulatory approvals, ie national regulatory approvals
- List of IRB/IEC Committee members/constitution
- Financial agreement(s)
- Documentation from central or local laboratory as applicable
 - Reference ranges
 - Certification/QA scheme/other documentation

Regulatory approval and notification as required must also be available; these are the responsibility of Shire HGT. All trial documents will be available in a Trial Master File (TMF) at the Investigator/trial site and at Shire HGT.

11.8 Data Monitoring Committee

There will be no data monitoring committee for this study.

11.9 Protocol Violations/Deviations

The Investigator will conduct the study in compliance with the protocol. The protocol will not be initiated until the IRB/IEC and the appropriate regulatory authorities have given approval/favorable opinion. Modifications to the protocol will not be made without agreement of the Sponsor. Changes to the protocol will require written IRB/IEC approval/favorable opinion prior to implementation, except when the modification is needed to eliminate an immediate hazard(s) to patients. The IRB/IEC may provide, if applicable regulatory authorities permit, expedited review and approval/favorable opinion for minor change(s) in ongoing studies that have the approval/favorable opinion of the IRB/IEC. The Sponsor will submit all protocol modifications to the regulatory authorities in accordance with the governing regulations. A record of patients screened, but not entered into the study, is also to be maintained.

When immediate deviation from the protocol is required to eliminate an immediate hazard(s) to patients, the Investigator will contact the Sponsor or its designee, if circumstances permit, to discuss the planned course of action. Any departures from the protocol must be fully documented as a protocol deviation. Protocol deviations will need to be reviewed by the medical monitor and may also be required to be submitted to the IRB/IEC

Protocol modifications will only be initiated by the Sponsor and must be approved by the IRB/IEC and submitted to the FDA or other applicable international regulatory authority before initiation.

11.10 Access to Source Documentation

Regulatory authorities, the IEC/IRB, or the Sponsor may request access to all source documents, CRFs, and other study documentation for on-site audit or inspection. Direct access to these documents must be guaranteed by the Investigator, who must provide support at all times for these activities. Monitoring and auditing procedures that comply with current GCP guidelines will be followed. On-site review of the CRFs for completeness and clarity, cross-checking with source documents, and clarification of administrative matters will be performed.

11.11 Data Generation and Analysis

The clinical database will be developed and maintained by a contract research organization or an electronic data capture technology provider as designated by Shire HGT. Shire HGT or its designee will be responsible for performing study data management activities.

Adverse events will be coded using Medical Dictionary for Regulatory Activities (MedDRA) Version 9.0 or later. Concomitant medication will be coded using WHODRL. Centralized laboratories will be employed as described in the study manual to aid in consistent measurement of efficacy and safety parameters.

11.12 Premature Closure of the Study

11.12.1 Study Termination

If the Sponsor or an Investigator discovers conditions arising during the study which indicate that the clinical investigation should be halted due to an unacceptable patient risk, the study may be terminated after appropriate consultation between Shire HGT and the Investigators. In addition, a decision on the part of Shire HGT to suspend or discontinue development of the study material may be made at any time.

11.12.2 Site Termination

A specific site may be terminated separate from the general study for, but not limited to, the following conditions:

- The discovery of an unexpected, significant, or unacceptable risk to the patients enrolled at the site.
- Failure of the Investigator to enter patients at an acceptable rate.
- Insufficient adherence by the Investigator to protocol requirements.

11.13 Retention of Data

Essential documents should be retained until at least 2 years after the last approval of a marketing application and until there are no pending or contemplated marketing applications or at least 2 years have elapsed since the formal discontinuation of clinical development of the investigational product. The Sponsor will notify the Investigator if these documents must be retained for a longer period of time. It is the responsibility of the Sponsor to inform the Investigator or institution as to when these documents no longer need to be retained.

11.14 Financial Disclosure

The Investigator should disclose any financial interests in the Sponsor as described in 21 CFR Part 54 prior to beginning this study. The appropriate form will be provided to the Investigator by the Sponsor, which will be signed and dated by the Investigator, prior to the start of the study.

11.15 Publication and Disclosure Policy

All information concerning the study material, such as patent applications, manufacturing processes, basic scientific data, and formulation information supplied by the Sponsor and not previously published are considered confidential and will remain the sole property of the Sponsor. The Investigator agrees to use this information only in accomplishing this study and will not use it for other purposes.

It is understood by the Investigator that the information developed in the clinical study may be disclosed as required to the authorized regulatory authorities and governmental agencies.

In order to allow for the use of the information derived from the clinical studies, it is understood that there is an obligation to provide the Sponsor with complete test results and all data developed in the study in a timely manner.

The Investigator and any other clinical personnel associated with this study will not publish the results of the study, in whole or in part, at any time, unless they have consulted with Shire HGT, provided Shire HGT a copy of the draft document intended for publication, and obtained Shire HGT's written consent for such publication. All information obtained during the conduct of this study will be regarded as confidential. Shire HGT will use the information for registration purposes and for the general development of the drug.

Appendix 1 Schedule of Events

Table 1 Study Assessments for Patients Who Have Received 6 Months of Treatment With rhHNS (Study HGT-SAN-055) (Dose Groups 1 and 2)

Assessment	Screening/ Baseline Visit ⁱ	Week 1 Each Treatment Month			12, 24, 36, and 48 months	End of Study ^f	Safety Follow-up ^h
		Pre-Tx Day 1 ^{a,1}	IT administration Day 2	Day 3 ^d			
Informed Consent/Enrollment		•					
Physical Examination	•	•	•			•	
Height and Weight	•	•				•	
Head Circumference	•				•	•	
Visual and Hearing Assessment					•	•	
ECG	•		• ^b			•	
Vital Signs	•	•	•	•		•	
Hematology	•	•				•	
Serum Chemistry	•	•				•	
Urinalysis	•	•				•	
Urine Heparan Sulfate and Heparan Sulfate Derivatives	•				• ^c	•	
Serum Heparan Sulfate and Heparan Sulfate Derivatives	•				• ^c	•	
Anti-rhHNS antibody testing (serum and CSF) ^j	•				•	•	
Auditory Brainstem Response (ABR)	•				•	•	
MRI of the Head	•				•	•	
CSF Sample Collection ^k	•		• ^c			• ^c	
rhHNS administration ^g			•				
Neurological Examination	•	•	•	•		•	
Full Neurodevelopmental Testing	•				•	•	
Children's Sleep Habits Rating Scale	•				•	•	
Child Health Questionnaire-50	•				•	•	
Child Health Questionnaire-87	•				•	•	
Infant Toddler QOL Questionnaire	•				•	•	

Table 1 Study Assessments for Patients Who Have Received 6 Months of Treatment With rhHNS (Study HGT-SAN-055) (Dose Groups 1 and 2)

Assessment	Screening/ Baseline Visit ⁱ	Week 1 Each Treatment Month			12, 24, 36, and 48 months	End of Study ^f	Safety Follow-up ^h
		Pre-Tx Day 1 ^{a,1}	IT administration Day 2	Day 3 ^d			
Concomitant Medications, Therapies, and Procedures	•	•	•	•		•	•
Adverse Event Monitoring	•	•	•	•		•	•

Abbreviations: ABR = Auditory brainstem response; CSF = cerebrospinal fluid; ECG = electrocardiogram; MRI = Magnetic resonance imaging;
 TX = treatment;

^a Week 1 only, and only performed if >7 days have elapsed since HGT-SAN-055 EOS visit assessments.

^b ECG to be performed following administration of study drug.

^c A total of 10 mLs of CSF will be obtained in two 5 mL aliquots (labeled separately – process according to study operations manual). An attempt will be made to obtain CSF sample via the IDDD prior to each administration of rhHNS and at the End of Study visit. If it is not possible to obtain CSF using the IDDD, the IDDD will be replaced. See [Section 6.4](#) for details.

^d Patients will be discharged when deemed clinically stable by the Investigator.

^e Specimens collected once a month, at Day 1 of the first treatment week.

^f All patients who complete the study will have end of study assessments performed 30 (±7 days) after their last dose of study drug.

^g If a patient’s IDDD becomes nonfunctional or infected; it will be replaced so that the patient can remain on study. See [Section 6.5](#).

^h A safety follow up telephone call will be made 30 (±7 days) after End of Study Procedures.

ⁱ Assessments will be required only if more than 60 days have elapsed following the HGT-SAN-055 procedures. These assessments would be repeated within 30 days prior to the first scheduled rhHNS IT dose.

^j Blood sample drawn before IT injection of rhHNS.

^k CSF will be tested for standard chemistries, heparan sulfate and heparan sulfate derivatives, anti-rhHNS antibodies, and MPS exploratory biomarkers.

Table 2 Study Assessments for Patients Who Have Received 6 Months of Treatment With rhHNS (Study HGT-SAN-055) (Dose Group 3)

Assessment	Screening/Baseline Visit ⁱ	Week 1 and 3 Each Treatment Month			12, 24, 36, and 48 months	End of Study ^f	Safety Follow-up ^h
		Pre-Tx Day 1 ^a	IT administration Day 2	Day 3 ^d			
Informed Consent/Enrollment		•					
Physical Examination	•	•	•			•	
Height and Weight	•	•				•	
Head Circumference	•				•	•	
Visual and Hearing Assessment					•	•	
ECG	•		• ^b			•	
Vital Signs	•	•	•	•		•	
Hematology	•	•				•	
Serum Chemistry	•	•				•	
Urinalysis	•	•				•	
Urine Heparan Sulfate and Heparan Sulfate Derivatives	•				• ^c	•	
Serum Heparan Sulfate and Heparan Sulfate Derivatives	•				• ^c	•	
Anti-rhHNS antibody testing (serum and CSF) ^j	•				•	•	
Auditory Brainstem Response (ABR)	•				•	•	
MRI of the Head	•				•	•	
CSF Sample Collection ^k	•		• ^c			• ^c	
rhHNS administration ^g			•				
Neurological Examination	•	•	•	• ^j		•	
Full Neurodevelopmental Testing	•				•	•	
Children's Sleep Habits Rating Scale	•				•	•	
Child Health Questionnaire-50	•				•	•	
Child Health Questionnaire-87	•				•	•	
Infant Toddler QOL Questionnaire	•				•	•	

Table 2 Study Assessments for Patients Who Have Received 6 Months of Treatment With rhHNS (Study HGT-SAN-055) (Dose Group 3)

Assessment	Screening/Baseline Visit ⁱ	Week 1 and 3 Each Treatment Month			12, 24, 36, and 48 months	End of Study ^f	Safety Follow-up ^h
		Pre-Tx Day 1 ^a	IT administration Day 2	Day 3 ^d			
Concomitant Medications, Therapies, and Procedures	•	•	•	•		•	•
Adverse Event Monitoring	•	•	•	•		•	•

Abbreviations: ABR = Auditory brainstem response; CSF = cerebrospinal fluid; ECG = electrocardiogram; MRI = Magnetic resonance imaging ;
 TX = treatment;

^a Week 1 only, and only performed if >7 days have elapsed since HGT-SAN-055 EOS visit assessments.

^b ECG to be performed following administration of study drug.

^c A total of 10 mLs of CSF will be obtained in two 5 mL aliquots (labeled separately – process according to study operations manual). An attempt will be made to obtain CSF sample via the IDDD prior to each administration of rhHNS and at the End of Study visit. If it is not possible to obtain CSF using the IDDD, the IDDD will be replaced. See [Section 6.4](#) for details.

^d Patients will be discharged when deemed clinically stable by the Investigator.

^e Specimens collected once a month, at Day 1 of the first treatment week.

^f All patients who complete the study will have end of study assessments performed 30 (±7 days) after their last dose of study drug.

^g If a patient’s IDDD becomes nonfunctional or infected; it will be replaced so that the patient can remain on study. See [Section 6.5](#).

^h A safety follow up telephone call will be made 30 (±7 days) after End of Study Procedures.

ⁱ Assessments will be required only if more than 60 days have elapsed following the HGT-SAN-055 procedures. These assessments would be repeated within 30 days prior to the first scheduled rhHNS IT dose.

^j Blood sample drawn before IT injection of rhHNS.

^k CSF will be tested for standard chemistries, heparan sulfate and heparan sulfate derivatives, anti-rhHNS antibodies, and MPS exploratory biomarkers.

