Patients whose parents/legal guardians provide written informed consent/assent to participate in this study will check in with the study center 1 day prior to rhHNS dosing for safety assessments on each rhHNS treatment week. If no safety concerns exist, the patient will subsequently receive IT administration of rhHNS on Day 2 (± 2 days). Patients will be discharged from the inpatient unit a minimum of 1 day following dosing with rhHNS and when deemed clinically stable by the Investigator.

The patient will have already received a standardized battery of neurodevelopmental assessments at the Baseline and 6-month time points in the HGT-SAN-055 study. These same assessments and tests will be performed at 12, 24, 36, and 48 months. Similarly, MRI of the head, ABR testing, CSF sampling by means of lumbar puncture and any other procedures requiring anesthesia will be performed at 12, 24, 36, and 48 months.

All patients will undergo end of study procedures 30 (\pm 7) days following their last administration of rhHNS. End of study procedures will include a standard battery of clinical laboratory tests (serum chemistry, hematology, and urinalysis) in CSF and blood, protocol specific laboratory testing (eg, anti-rhHNS antibody testing), neurodevelopmental testing, ABR, child health questionnaires, MRI, and concomitant medications and AE monitoring.

All patients will be contacted by telephone for a Final Safety Follow-up, to be conducted at 30 (\pm 7) days after the EOS procedures to collect updated information on adverse events and concomitant medications, therapies, and procedures.

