6.3 Selection and Timing of Dose for Each Subject

The patient's dose of rhHNS will be the same dose (10 mg and 45 mg once per month and 45 mg EOW) they received in Study HGT-SAN-055. Patients will check in to the study center 1 day prior to intrathecal rhHNS dosing for safety assessments on each rhHNS treatment week, and if no safety concerns exist, will subsequently receive IT administration of rhHNS on Day 2. Patients will be discharged from the inpatient unit a minimum of 1 day following dosing with rhHNS and when deemed clinically stable by the Investigator.

The IT injections are to be administered 28 days (± 7 days [groups 1 and 2]) and 14 days (± 3 days [group 3]) apart. If a patient's IDDD becomes nonfunctional, it will be replaced so that the patient can remain on study. See [Section 6.5](#) for a description on the replacement of a nonfunctional IDDD.

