7 STUDY PROCEDURES

7.1 Informed Consent

Study procedures will be conducted only after written informed consent for the patient to participate in this study is provided by the parent(s) or legal guardian(s) and assent from the patient (if applicable). Detailed descriptions of patient evaluations required for this protocol are described in this section. These evaluations will be performed during the indicated days and weeks of each study month (see [Appendix 1](#) Schedule of Events).

All data collected are to be recorded on the appropriate eCRF. The approximate maximum total blood, urine, and CSF volumes to be collected from each patient by the end of this study for safety assessments are presented in Table 7-1.

Table 7-1 Approximate Total Sample Volumes Collected Over the Duration of the Study From Each Patient by Group and Assay

	Groups 1 and 2	Group 3
Blood	290 mL	555 mL
Urine	530 mL	1,010 mL
CSF	480 mL	960 mL

Blood, urine and CSF volumes to be collected for each clinical laboratory measurement are described in detail in the Laboratory and/or Study Operations Manual.

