8.2.1 Week 1 (Groups 1 and 2); Week 1 and 3 (Group 3)

8.2.1.1 Day 1 (Pre-treatment) Assessments

- Informed consent (Week 1, Month 1 only) prior to study HGT-SAN-067 study procedures
- Physical examination
- Height and weight
- Vital signs
- Hematology
- Serum Chemistry
- Urinalysis
- Neurological Examination (performed prior to the administration of anesthesia and the rhHNS IT injection)
- Concomitant Medications, Therapies, and Procedures
- AE assessments

Note: If the HGT-SAN-055 EOS (or Screening) assessments were performed within 7 days of first intrathecal rhHNS treatment in this study, the pre-treatment assessments described in this section do not need to be completed prior to the first treatment

DAY 1 (PRE-TREATMENT) ADDITIONAL ASSESSMENTS PERFORMED ONLY AT MONTHS 12, 24, 36, AND 48

- Head circumference
- Visual and hearing assessments
- Urine Heparan Sulfate and Heparan Sulfate Derivatives (Group 3: obtained only at first week of each treatment month)
- Serum Heparan Sulfate and Heparan Sulfate Derivatives (Group 3: obtained only at first week of each treatment month)

- Anti-rhHNS antibody testing
- Auditory Brainstem Response (ABR)
- MRI of the head
- Full neurodevelopmental testing (performed prior to the administration of anesthesia and the rhHNS IT injection)
- Children's Sleep Habits Rating Scale
- Child health questionnaire-50
- Child health questionnaire-87
- Infant toddler QOL Questionnaire

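### Appendix 1 footnote a limits the pre-dose Day 1 tests to Week 1, against the Table 2 heading and Sections 4.1, 6.3 and 8.2.1, which call for them in every treatment week

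*Protocol*

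**What the plan says.** Footnote a is attached to the pre-treatment Day 1 column of Table 1 (Groups 1 and 2) and Table 2 (Group 3) in Appendix 1, with the same text in the original protocol and in Amendment 1: "Week 1 only, and only performed if >7 days have elapsed since HGT-SAN-055 EOS visit assessments". The heading over that column is "Week 1 Each Treatment Month" in Table 1 and "Week 1 and 3 Each Treatment Month" in Table 2.

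The body text says otherwise for Group 3. Section 6.3 states: "Patients will check in to the study center 1 day prior to intrathecal rhHNS dosing for safety assessments on each rhHNS treatment week". Section 4.1 has the same requirement: patients "will check in with the study center 1 day prior to rhHNS dosing for safety assessments on each rhHNS treatment week". Section 8.2.1 heads its Day 1 list, which includes hematology, serum chemistry and urinalysis, as applying to Week 1 in Groups 1 and 2 and to Weeks 1 and 3 in Group 3. The only relief is in the Note to Section 8.2.1.1: if the HGT-SAN-055 end-of-study or Screening assessments fell within 7 days of the first extension dose, the Day 1 assessments "do not need to be completed prior to the first treatment".

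Section 7.1 sends the reader to Appendix 1 for the days and weeks on which evaluations are done. Nothing in the text shown says which prevails when the appendix and the body disagree.

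**The concern.** Hematology, serum chemistry and urinalysis are named in the primary safety endpoint (Section 3.1). In Table 2 the footnoted column is the only on-treatment column in which they are marked. A site working from the schedule, as Section 7.1 invites it to do, could follow the footnote and give doses without a current blood and urine safety set. Those results would then also be missing from the visit-by-visit laboratory summaries planned in Section 10.6.1.

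**Working it through.** **1. What depends on the footnoted column.** Between Screening and End of Study, Table 2 marks hematology, serum chemistry, urinalysis, and height and weight only under pre-treatment Day 1. Physical examination, vital signs, neurological examination and CSF collection are also marked on Day 2, which does not carry footnote a. Section 7.7.4.1 has chemistries and cell counts run on each CSF sample.

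**2. The statements for Group 3, side by side.**
- Table 2 heading: Weeks 1 and 3 of each month.
- Sections 4.1 and 6.3: every treatment week.
- Section 8.2.1: Weeks 1 and 3.
- Section 8.2.1.1 Note: a waiver for the first treatment only.
- Footnote a: Week 1.

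Only the footnote excludes Week 3.

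**3. What it probably meant.** The 7-day clause can matter only at the first extension dose. Under Section 6.3 the shortest interval to a second dose is 14 − 3 = 11 days in Group 3, so from then on more than 7 days have always passed since the HGT-SAN-055 visit. After the first dose the Week 1 limit is therefore the only part of the footnote with any effect. The same 7-day rule appears, correctly confined to the first dose, in the 8.2.1.1 Note. A garbled copy of that waiver is the likely origin.

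**4. The two literal readings.**
- Week of the month: Group 3 has two doses a month and would be tested before one of them, so 1/2 of its doses lose the blood and urine set. Table 1 is already headed Week 1, so Groups 1 and 2 lose nothing. If the last set was drawn the day before the Week 1 dose, its age at the Week 3 dose is 1 + 14 = 15 days (1 + 11 = 12 to 1 + 17 = 18 with the ±3-day window), instead of about 1 day.
- Week 1 of the study: every group loses the routine pre-dose set after the first extension dose.

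**5. Does Table 7-1 settle the intent?** Group 3 against Groups 1 and 2:
- Blood: 555/290 = 1.91.
- Urine: 1,010/530 = 1.91.
- CSF: 960/480 = 2.00.

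With Week 1 testing only, Group 3's blood total should be close to 290 mL; the table gives 555 mL, a difference of 265 mL. Serum heparan sulfate sampling does not explain this, because in Group 3 it is confined to the first week of the month, and the annual and end-of-study columns are the same for all groups. The blood total is therefore consistent with testing at every dose.

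It cannot be pushed further:
- Urine: Section 7.7.3.2 reserves a urine sample from each visit for exploratory work, so the urine total could nearly double without urinalysis at Week 3.
- Dose counts: 480/10 = 48 and 960/10 = 96 are inferred from CSF at 10 mL per dose. At the intervals in Section 6.3, four years gives 4 × 365.25/28 = 52 and 4 × 365.25/14 = 104. The original protocol also counts HGT-SAN-055 treatment within the four years, which would give fewer.
- Urine per visit: (1,010 − 530)/(96 − 48) = 10 mL, leaving 530 − 480 = 50 mL. Two unknowns taken from two totals always fit.
- Blood per visit: 265/48 = 5.52 mL, leaving 290 − 48 × 5.52 = 25 mL. Section 7.16 takes two 5 mL samples at each designated time point; months 12, 24, 36, 48 and End of Study alone would need 5 × 10 = 50 mL. The split does not agree with the stated volumes.

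**The case against.** The strongest defence is that nobody should read the footnote literally. Its second clause concerns only the first extension dose, the 8.2.1.1 Note states that rule properly, and four other places call for testing in every treatment week. When the authors wanted a once-a-month limit, footnote e says so in different words. This stands as evidence of intent and keeps the severity low. It does not make the footnote agree with the heading above it.

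A second objection is status. The title page lists amendments up to Amendment 8, and only the original protocol and Amendment 1 are shown here, so the footnote may have been corrected. That cannot be checked, and the point is limited to the text at hand.

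A third is that the tables' note marks are not wholly reliable: the Table 1 column header carries a second mark with no matching note. Footnote a, however, is on this column in both tables of both versions, so a stray mark is unlikely.

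Three stronger inferences are tempting and are not supported. Table 7-1 does not prove testing at every dose, nor does it show that 48 of 96 sets would be lost, because the per-visit volumes and dose counts are inferred. The effect is not confined to Group 3 unless Week 1 means week of the month. And nothing shows that any site actually omitted a test.

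**Conclusion.** Wrong as written; minor. Footnote a contradicts the Table 2 heading and Sections 4.1, 6.3 and 8.2.1. Its size depends on which literal reading a site adopts: half of Group 3's doses, or every dose after the first extension dose in all groups. The one-half figure needs only the two-doses-a-month schedule, not a total dose count.

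The loss under either reading is partial, because the Day 2 examinations, vital signs and CSF tests remain. The requirement itself is not in real doubt, since the rest of the protocol agrees on it. The nearly doubled Group 3 blood volume in Table 7-1 supports that view but does not carry the conclusion.

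**What to change.** Reword footnote a in Tables 1 and 2 of Appendix 1 to: Performed before every dose (Week 1; Weeks 1 and 3 for Group 3). May be omitted before the first extension dose only, if HGT-SAN-055 EOS (or Screening) assessments were done within 7 days.

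The cost is one footnote in two tables. It adds no sampling beyond what Section 8.2.1 already requires. If a later amendment already carries this correction, nothing further is needed.
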